4.1.8. Overall survival (OS)

Overall survival (OS): defined as the time from the date of first dose to death due to any cause.

Censoring rules are as follows:

- If there is no death or dropout by the end of study, the censoring date will be the last date when the survival status (alive) is obtained.

4.1.9. Change in tumor size (CTS)

The difference in tumor size from baseline as a percentage of baseline tumor size will be calculated based on the maximum decrease in tumor size or the minimum increase in tumor size after baseline.

Tumor size is defined as the sum of the longest diameters of target lesions assessed as per RECIST v1.1.

4.2. Safety Endpoints

The following safety data will be collected and summarized following the study protocol:

- Adverse events
- Laboratory test data
- Vital signs data
- ECOG PS
- ECG
- Physical examinations
- Other safety endpoints

4.2.1. Adverse events

Treatment-emergent adverse events (TEAEs) are defined as adverse events that occur on or after the day of the first study treatment.

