8.2.2 Progressive disease and death

Progressive disease (PD) is defined as the deterioration of the subject's conditions caused by the primary tumor targeted by the study drug, including radiological progressions and progressions in clinical symptoms and signs. New metastases relative to the primary tumor or progressions of the previous metastases are recognized as PD. Life-threatening events, hospitalization or prolonged hospitalization, permanent or serious disability/incapacity/impairment of work ability, congenital anomalies or birth defects resulting from signs and symptoms of progressive disease should not be reported as SAEs on an expedited basis. Death caused by the symptoms and signs of PD should be reported as an SAE on an expedited basis.

Death of a subject during the study, regardless of whether a new anti-tumor treatment is administrated, must be reported as an SAE. Deaths caused by symptoms and signs of PD as determined by the investigator shall be recorded in the eCRF and reported as SAEs. The term "death" shall not be used as an AE or SAE, but an outcome of an event. Events that result in death shall be recorded as AEs or SAEs. If the cause of death is unknown and cannot be determined at the time of reporting, the AE or SAE term "death of unknown cause" shall be used for documentation.

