8.3 Collection and Follow-Up of AEs/SAEs

The collection of AEs/SAEs should start from the time when the subjects sign the informed consent form and end 90 days after the last dose of SHR-1210 or 30 days after the last dose of anti-angiogenic targeted therapy (whichever is longer). SAEs occurring after this period that are suspected to be related to the study drug should be collected. See [Table 8-1](#) below for specific requirements. Any AE/SAE should be followed-up until the event resolves, returns to the baseline level or \leq Grade 1, reaches a steady state, or is reasonably explained (e.g., lost to follow-up, death). The investigator should try to obtain the best outcome and clear causality with the study drug.

During each visit, the investigator should ask about the situation of AEs/SAEs that occur after the last visit and provide follow-up information in a timely manner based on the sponsor's query request.

Table 8-1. Collection period of AEs/SAEs

Classification	Collection/Recording Requirements
AEs Unrelated to the Study Drug	Up to 30 days after the last dose
Treatment-Related AEs ^a	Up to 90 days after the last dose of SHR-1210 or 30 days after the last dose of apatinib (whichever is longer)
SAEs Unrelated to the Study Drug ^a	
 Fatal SAEs: up to 90 days after the last dose of SHR-1210 or 30 days after the last dose of apatinib (whichever is longer) Non-fatal SAEs: up to 30 days after the last dose
Treatment-Related SAEs ^b	No time limit

^a Non-serious AEs

^b Including fatal and non-fatal SAEs.

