5.4.3. Adverse events

AEs will be classified by treatment stage (before and after study treatment).

All AEs will be coded using MedDRA V24.0 and graded using NCI-CTCAE v4.03. Subject will be counted only once, even if the subject experiences more than one event within the same system organ class (SOC) and/or preferred term (PT). For the same AE reported in one subject multiple times but varying in CTCAE grade, the highest grade will be counted.

AEs will be ordered by descending incidence of SOC, and by descending incidence of PT within each SOC. If the incidence of ≥ 2 PTs is equal, the AEs will be ordered alphabetically. If there is no AE under a SOC or PT, the analysis will not be conducted.

Only TEAEs will be summarized. All AEs will be listed. AEs with completely missing onset time will be treated as TEAEs.

For AEs occurring after the start of study treatment, treatment-related AEs include those whose causality with the study drug is related, possibly related, or unassessable; if the causality assessment is missing, then the AE will be deemed treatment-related for analysis. AEs with any missing CTCAE grade will be analyzed based on the highest grade.

In AE summary table, AEs after study drug treatment will be analyzed according to the population/cohort, and the frequency and proportion will be used for statistical description. Analyses of AEs include but are not limited to the following:

- Any TEAE
- Treatment-related TEAE
- Any treatment-emergent serious adverse event (TESAE)
- Treatment-related TESAE
- CTCAE Grade ≥ 3 TEAE
- CTCAE Grade ≥ 3 treatment-related TEAEs
- Any TEAE with an incidence of $\geq 5\%$
- Treatment-related TEAE with an incidence of $\geq 5\%$
- AEs leading to treatment discontinuation
- Treatment-related AEs leading to treatment discontinuation
- AEs leading to discontinuation of SHR-1210
- Treatment-related AEs leading to discontinuation of SHR-1210
- AEs leading to discontinuation of apatinib
- Treatment-related AEs leading to discontinuation of apatinib
- AEs leading to interruption of SHR-1210
- Treatment-related AEs leading to interruption of SHR-1210
- AEs leading to interruption of apatinib
- Treatment-related AEs leading to interruption of apatinib
- AEs leading to dose reduction of apatinib
- Treatment-related AEs leading to dose reduction of apatinib
- AEs leading to death
- Treatment-related AEs leading to death
- TEAEs of special interest (SIEs, see Appendix 2 for specific classification)

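### The SAP sets no end to the treatment-emergent period, and the protocol's death-reporting rules conflict, so late deaths from disease can enter the adverse event tables

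*SAP*

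**What the plan says.** **SAP.** Section 4.2.1 reads "Treatment-emergent adverse events (TEAEs) are defined as adverse events that occur on or after the day of the first study treatment". It gives no last day and no cut at the start of another anti-tumor treatment. Section 5.4.3 adds no filter: "Only TEAEs will be summarized. All AEs will be listed". The planned rows include "Any treatment-emergent serious adverse event (TESAE"), Grade ≥3 events, events leading to death and "Treatment-related AEs leading to death". The same section says that "if the causality assessment is missing, then the AE will be deemed treatment-related for analysis".

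**Protocol 8.2.2.** "Death of a subject during the study, regardless of whether a new anti-tumor treatment is administrated, must be reported as an SAE". For progressive disease: "Deaths caused by symptoms and signs of PD as determined by the investigator shall be recorded in the eCRF and reported as SAEs". Neither sentence carries a day limit.

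**Protocol 8.2.4.** For subjects who start other anti-tumor treatment, this section points to Section 8.3. It requires prompt reporting of a post-treatment death that falls inside the SAE reporting period.

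**Protocol 8.3, Table 8-1.** For SAEs unrelated to the study drug: "Fatal SAEs: up to 90 days after the last dose of SHR-1210 or 30 days after the last dose of apatinib", whichever is longer. Unrelated non-fatal SAEs and unrelated AEs stop at 30 days after the last dose. Related non-serious AEs run to the 90/30-day limit, and related SAEs have no time limit.

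**Follow-up.** Survival contacts continue every 2 months until death (Protocol 7.4). Follow-up runs to 12–24 months after the last subject's last dose (Protocol 5.4; Section 13.4 counts from that subject's first dose).

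**The concern.** Sites will learn of deaths long after treatment has stopped, and the protocol gives them two instructions. Under 8.2.2 such a death is an SAE. Under 8.2.4 and Table 8-1 an unrelated death past the limit is not collected as one. The SAP should be the backstop but has no cut-off of its own, so whatever is entered is counted. For efficacy the SAP does stop the clock: ORR, BOR, DoR and PFS are all cut at new anti-tumor treatment.

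Incidence and severity of AEs and SAEs is the Stage I primary endpoint and a Stage II secondary endpoint. If late disease deaths enter, the serious, Grade ≥3 and fatal rows drift toward overall mortality. They would then depend on which rule a site followed and how long its subjects were followed. The SAP also sets 250 mg beside 375 mg on serious and Grade ≥3 events, and unequal follow-up could affect that comparison. The documents give no basis for sizing that effect.

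A second, smaller issue does not depend on the death rule. After day 30, Table 8-1 admits non-fatal events only if they are judged related, so an open-ended row for any TEAE mixes two standards of ascertainment.

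**Working it through.** The documents state no count or rate on this point, so there is no figure to reproduce. The check is a comparison of the rules, followed by an illustration of size.

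**1. Which events reach the tables**

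| Event | Protocol 8.2.2 read literally | 8.2.4 and Table 8-1 | SAP, if recorded |
|---|---|---|---|
| Unrelated death within the 90/30-day limit | SAE | SAE | Counted |
| Unrelated death after the limit, on later therapy | SAE | Not collected | Counted |
| Related death after the limit | SAE | SAE, no time limit | Counted |
| Unrelated non-fatal event after day 30 | Not addressed | Not collected | – |
| Related non-fatal AE, day 31 to the limit | Not addressed | Collected | Counted |

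The conflict is confined to the second row. Take a subject who dies of progression 10 months after the last dose while on another therapy. If the site follows 8.2.2, this is a treatment-emergent SAE, a Grade 5 event (so in the Grade ≥3 row) and an AE leading to death. If the site follows Table 8-1, it appears in none of these. If the death is entered without a causality assessment, SAP 5.4.3 places it in the treatment-related rows as well.

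**2. Ceiling on the size**

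All survival inputs are assumptions:
- overall survival is exponential with median 12, 15 or 18 months, hazard h = ln 2 / median;
- time to stopping treatment is independent and exponential with median 4, 6 or 8 months, hazard k = ln 2 / median, and treatment is cut at death or month 24;
- follow-up is 24 months from first dose;
- both drugs stop together, so the limit is w = 90/30.4375 = 2.957 months after the last dose.

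Deaths by month 24: 1 − exp(−24h).

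Deaths by month 24 but later than w after the last dose:

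L = exp(−hw) − exp(−24h) − exp(−hw) × h/(h+k) × [1 − exp(−(h+k)(24−w))].

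Worked case, survival median 15 and treatment median 6: h = 0.0462, k = 0.1155, exp(−hw) = 0.872, exp(−24h) = 0.330, h/(h+k) = 0.286 and the bracket is 0.967. So L = 0.872 − 0.330 − 0.872 × 0.286 × 0.967 = 0.301. Deaths by month 24 are 67.0%, of which 67.0 − 30.1 = 36.9 points fall on treatment or within 90 days.

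| OS median (months) | Treatment median (months) | Dead by month 24 | On treatment or within 90 days | Later |
|---|---|---|---|---|
| 12 | 4 | 75.0% | 36.6% | 38.4% |
| 12 | 8 | 75.0% | 47.8% | 27.2% |
| 15 | 6 | 67.0% | 36.9% | 30.1% |
| 18 | 4 | 60.3% | 26.8% | 33.5% |
| 18 | 8 | 60.3% | 36.2% | 24.1% |

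The last column, about 24–38 points, is what the fatal-event row gains if every late death is entered as an SAE. If a tenth are entered, the gain is 2.4–3.8 points. If none are, it is 0.

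**3. Cross-check from the last dose**

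Assume exponential survival from the last dose with median m. The share of post-treatment deaths by month F that fall after day 90 is [exp(−hw) − exp(−hF)] / [1 − exp(−hF)], with h = ln 2 / m. For m = 6 and F = 12 this is (0.711 − 0.250)/0.750 = 61%. Over m = 3 to 18 and F = 12 or 24 it runs from 47% to 82%. So under either rule a large part of post-treatment deaths lies in the disputed period.

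**The case against.** The best defence is that the protocol already bounds collection. The AE definition in 8.1.1 defers to Section 8.3 for the collection period. Section 8.3 ends collection at the 90/30-day limit and admits later SAEs only if suspected related. Section 8.2.4 covers subjects on other therapy directly, and SAP 4.2 says safety data are collected and summarized following the protocol. If these specific rules limit the general sentence in 8.2.2, a late unrelated death is never recorded as an SAE and cannot be treatment-emergent.

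That reading is reasonable, and it defeats several stronger conclusions a reader might draw:

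- *Late deaths will be counted.* The documents support only that they can be, where 8.2.2 is followed literally.
- *The distortion is 24–38 points.* That is a ceiling with every late death entered, on survival inputs the documents do not give. For the serious and Grade ≥3 rows even the ceiling is lower if some of these subjects already had such an event.
- *The dose decision is compromised.* It rests on clinically significant toxicity in the first 28 days, in its own analysis set.
- *All deaths under later therapy breach Table 8-1.* Those inside the limit, and related deaths at any time, are consistent with it.

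It is also fair that late deaths judged unrelated stay out of the treatment-related rows, that the safety output is descriptive, and that the longer collection of related events is Table 8-1's design rather than the SAP's.

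The defence does not remove the defect. Section 8.2.2 has no day limit and expressly reaches past new therapy, so 8.2.4 is one side of a contradiction. The SAP's deference to an inconsistent protocol does not supply the missing end date.

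**Conclusion.** The point holds in limited form. The SAP's treatment-emergent period has no end, and Protocol 8.2.2 conflicts with 8.2.4 and Table 8-1 on unrelated deaths after the 90/30-day limit. Late disease deaths can therefore enter the serious, Grade ≥3 and fatal-event tables, and with missing causality they would be analysed as treatment-related.

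The effect on the fatal-event row ranges from 0, if sites follow Table 8-1, to about 24–38 percentage points, if every late death is entered. The upper figure rests on exponential survival with medians of 12–18 months, treatment medians of 4–8 months and 24 months of follow-up, all assumed. The difference in ascertainment after day 30 follows from Table 8-1 whichever death rule is used. A correction should be made before database lock.

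**What to change.** **SAP 4.2.1.** End the treatment-emergent period at the Section 8.3/Table 8-1 limit: 90 days after the last SHR-1210 dose or 30 days after the last apatinib dose, whichever is longer. Use this single window for both the all-event and the treatment-related tables. A 30-day window for one and a 90-day window for the other would leave related events from day 31 onward missing from the all-event table, and would drop unrelated fatal SAEs that Table 8-1 collects.

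**SAP 5.4.3.**
- Add a sensitivity summary of all treatment-emergent events to 30 days after the last dose, where related and unrelated events are both collected.
- List related SAEs after the window separately.
- Add a table of all deaths by cause (with an unknown category) and by time since last dose. Identify deaths from progression inside the window rather than removing them.

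**Protocol.** Sections 8.2.2, 8.2.4 and 8.3 must be reconciled on the reporting period for deaths. The SAP cut-off protects the tables whichever reporting rule is kept.

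**Cost.** The SAP changes are wording and one or two extra outputs, with no new data. The protocol change is an amendment and needs ethics committee approval (Protocol 11.2). The downside is that some late events move from summary tables to listings.

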- [11] Hepatitis B, hepatitis C, and HIV tests: hepatitis B panel [If the test results are abnormal, viral replication (HBV DNA) test should be performed]; hepatitis C virus antibody (anti-HCV) test (If the test results are abnormal, virus titer should be tested); HIV antibody test.
- [12] Pregnancy test: The urine pregnancy test will be performed 72 h before the first dose for females of a childbearing age. If the result of the urine pregnancy test is positive, a serum pregnancy test shall be performed. If necessary, re-tests can be performed for confirmation.
- [13] If the subjects have previously been tested for EGFR mutations and ALK fusion gene, retests are not required; otherwise, the study site will perform relevant tests. If the subjects are positive for EGFR mutations, the test of ALK fusion gene will no longer be performed.
- [14] Adverse events: Adverse events will be collected from the time when the subjects sign the informed consent form. AEs unrelated to the study drugs will be collected to 30 days after the last dose. Treatment-related AEs will be collected until 90 days after the last dose of SHR-1210 or 30 days after the last dose of targeted anti-angiogenic therapy (whichever is longer). See the AE/SAE collection time limit in Section 8.3 for details.
- [15] Vital sign examination: Body temperature, respiration, pulse, blood pressure. The examination will be performed within 7 days before enrollment, on Day 1 and Day 15 of Cycle 1, Day 1 and Day 15 of subsequent cycles, upon completion of the study, and 30 days after treatment.
- [16] Physical examination and weight measurement: Examination of major body systems (head and face, skin system, lymph nodes, eyes, ears, nose, throat, oral cavity, respiratory system, cardiovascular system, abdomen, urogenital system, musculoskeletal system, nervous system and mental state) will be performed within 7 days before enrollment, on D1 and D15 of Cycle 1, D1 and D15 of subsequent cycles, upon completion of the study, and 30 days after the end of treatment. Body weight measurement will be started on D1 of Cycle 1 and performed on D1 of subsequent cycles, upon completion of the study, and 30 days after the end of treatment.
- [17] 12-Lead ECG: Performed within 7 days before enrollment, on Day 15 of Cycle 1, Day 1 and Day 15 of subsequent cycles, and upon completion of the study. Abnormalities in ECG must be confirmed twice via additional ECG tests.

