8 SAFETY EVALUATION

8.1 Adverse Events (AEs)

8.1.1 Definition of adverse event

An adverse event (AE) refers to any untoward medical occurrence in a study subject administered a medicinal product and which does not necessarily have a causal relationship with this treatment. For the specific period of AE collection in this study, please refer to Section 8.3. AEs include the following:

- 1) Worsening of pre-existing (prior to entering clinical study) medical conditions/diseases (including worsening symptoms, signs, or laboratory abnormalities);
- 2) Any new AEs: Any new adverse medical conditions (including symptoms, signs, and newly diagnosed diseases);
- 3) Clinically significant abnormal laboratory findings.

The investigator should record any AEs that have occurred in detail, including the description of the AEs and all relevant symptoms, time of occurrence, severity, causality with the study drugs, duration, measures taken, and final results and outcomes.

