5.1.5.2. Adverse events

If the date related to an AE is missing, the rules for imputing are as follows:

- If the start date of an AE is completely missing, the date will be imputed with the date of the first administration.
- If only the day of the start date of the AE is missing with the same year and month as those of the first administration, the day will be imputed with that of the date of the first administration.
- If both the month and day of the start date of the AE are missing with the same year as that of the first administration, the month and day will be imputed with those of the date of the first administration.
- In other cases, if the month or day of the start date of the AE is missing, it will be imputed with 1.

- If only the day of the end date of the AE is missing, the date will be imputed with the last day of the month (before the date of death). If the last day of the month is later than the date of death, it will be imputed with the date of death.
- In other cases, if the end date of the AE is missing, the date will not be imputed.

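### SAP 4.2.1 has no worsening clause, so an AE that starts in screening and worsens on study drug can miss the TEAE tables, while the start-date rule in SAP 5.1.5.2 can err the other way

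*SAP*

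**What the plan says.** SAP 4.2.1 gives the definition: "Treatment-emergent adverse events (TEAEs) are defined as adverse events that occur on or after the day of the first study treatment". SAP 5.4.3 sorts AEs into two stages, before and after study treatment, and continues: "Only TEAEs will be summarized. All AEs will be listed. AEs with completely missing onset time will be treated as TEAEs". The same section defines treatment-related AEs only among those that occur once treatment has started.

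Collection begins earlier. Note [14] to the Schedule of Activities in the protocol reads: "Adverse events will be collected from the time when the subjects sign the informed consent form". Protocol 8.3 sets the same start. Screening runs from D-21 to D-1 (Protocol 7.1), and in Cohort 4 it may run longer while the TMB result is awaited.

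Protocol 8.1.1 includes among AEs: "Worsening of pre-existing (prior to entering clinical study) medical conditions/diseases (including worsening symptoms, signs, or laboratory abnormalities".

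For missing dates, SAP 5.1.5.2 says: "If the start date of an AE is completely missing, the date will be imputed with the date of the first administration". Where the day alone is missing, and the month and year are those of first administration, "the day will be imputed with that of the date of the first administration". If month and day are missing and the year matches, both come from first administration. For any other incomplete start date, the missing part becomes 1.

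**The concern.** Incidence and severity of AEs and SAEs is the Stage I primary endpoint and a Stage II secondary endpoint (Protocol 2.2). A low-grade event that begins after consent and becomes severe on study drug is toxicity information, and a reader would expect to find it in the TEAE tables. Under a definition based on when the event occurs, it can be classed as a pre-treatment event and only listed.

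The setting makes this plausible. The protocol background names hypertension and proteinuria as apatinib reactions, and hypothyroidism and raised transaminases for SHR-1210. Eligibility lets a subject start dosing with abnormal TSH if FT3 and FT4 are normal, with ALT or AST up to 1.5 x ULN, or with urine protein of ++ if the 24-hour quantity is not above 1.0 g.

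The imputation rule raises the opposite worry: an event that was over before dosing could be counted as treatment-emergent.

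**Working it through.** The plan states no figure on this point, so the check is a reading of the text followed by a scale calculation.

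**1. Can pre-dose AEs be in the database?** Yes. Collection starts at consent, and screening lasts up to 21 days, or longer in Cohort 4.

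**2. Which date decides TEAE status?** Onset. SAP 4.2.1 asks when the event occurs, and SAP 5.4.3 treats a wholly missing onset time as treatment-emergent. SAP 5.1.5.2 handles start and end dates but no date of worsening. There is no category for an AE that started before first dose and worsened after it.

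**3. Does another rule bring such an event back?**
- Protocol 8.1.1 makes worsening an AE in its own right for conditions present before study entry. If entry means consent, an AE that began after consent is not covered. If entry means inclusion at the end of screening, it is. The protocol does not say which.
- SAP 5.4.3 takes the highest grade when one AE is reported several times. That fits a practice of opening a new record at each grade change, but does not require it.

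**4. Which outputs still show the event?**

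| Output | Shows worsening? |
|---|---|
| AE listings (SAP 5.4.3) | Yes, all AEs are listed |
| Stage I clinically significant toxicity table (SAP 5.4.2) | Yes, if the event qualifies; it uses the DLT set and does not refer to TEAEs, but covers only the four-week observation period |
| Laboratory shift tables (SAP 5.4.4) | In part; they use clinical significance, not CTCAE grade, so a result already clinically significant at baseline that rises in grade shows no shift |
| Vital signs (SAP 5.4.5) | Only as group statistics by visit |
| Symptoms such as cough | No other summary |

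**5. Scale of one subject** (planned sizes from SAP 2.3, groupings from SAP 5):
- Cohort 4: 1/20 = 5.0%, which equals the cut-off of the SAP 5.4.3 tables for events with incidence of at least 5%.
- Cohort 2 or 3: 1/38 = 2.6%.
- Cohort 1: 1/78 = 1.3%.
- Pooled driver gene negative population: Cohorts 1 and 3 alone give 78 + 38 = 116, so at most 1/116 = 0.9%.

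**6. The date rule.** Suppose first dose is on day d of a month, an AE start date is known only to that month, and its end date is recorded as day e of the same month, with e < d. The imputed start is d, so the event starts after it ended. Its duration, e - d + 1, is zero or negative, yet it counts as a TEAE. The same happens when the start is wholly missing, or is known only to the year of first dose, and the recorded end precedes first dose. No check against the end date is stated. A missing day in an earlier month is set to 1 and correctly stays before dosing.

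**The case against.** The strongest reply is that the loss is not established. Protocol 8.1.1 can be read to cover screening-onset conditions, because eligibility is verified again before a subject is included (Protocol 7.1). Data entry also follows an eCRF completion guide (Protocol 11.4.1) that is not part of these documents. If that guide opens a new record at each grade increase, the worsened event has an on-treatment start and is counted. This stands as a condition on the finding. It does not remove the finding, because neither document states the convention and the SAP definition does not depend on it.

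Three stronger readings are tempting and are not supported:
- *The event disappears from every AE summary.* It stays in the listings, and the Stage I toxicity table, which bears on the tolerability decision, is not tied to the TEAE definition. Some laboratory worsening also shows in the shift tables.
- *One lost subject moves a Stage I dose-group AE rate by 8 to 10 points.* That divides by the 10 to 12 tolerability subjects (1/12 = 8.3%, 1/10 = 10.0%). A tolerable dose group is planned to take another 10 to 12 PK subjects, giving 20 to 24 in all and 4.2% to 5.0% per subject. SAP 5 also pools Stage I subjects on 250 mg with Stage II cohorts.
- *The bias simply favours the drug.* The missing worsening clause does lower reported rates. The imputation rule raises them. It can be defended as conservative when nothing is known of timing, but not when a recorded end date already places the event before dosing.

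**Conclusion.** The point holds in a limited form. As written, the SAP leaves a screening-onset AE that rises in grade or becomes serious on study drug out of the TEAE-based tables (any, related, Grade >=3, serious), unless sites open a new record at worsening. Whether they do cannot be seen from the documents. The documents give no rate of screening-onset AEs that worsen, so the number affected cannot be estimated; it is probably small. The effect is most visible in Cohort 4, where one subject is enough to put a term on or off the table of events with incidence of at least 5%.

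The imputation rule is a separate error in the opposite direction, limited to the three missing-date patterns it names and to events whose recorded end precedes first dose. The two errors affect different events and should not be assumed to cancel. Because both touch the Stage I primary and a Stage II secondary endpoint and cost little to correct, the SAP should be changed.

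**What to change.** **SAP 4.2.1**, replace the definition with: *TEAE = an AE with onset on or after first dose, or an AE with earlier onset that increases in CTCAE grade or becomes serious on or after first dose, counted at its post-dose grade.*

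**SAP 5.1.5.2**, add: *an imputed start date may not be later than the recorded end date, and an AE that ended before first dose is not a TEAE.* The sentence in SAP 5.4.3 on wholly missing onset times needs the same exception.

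**eCRF completion guide**, only if the eCRF does not date grade changes: add one line telling sites to open a new record when an AE worsens.

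The cost is two SAP sentences with a matching exception, a little programming, and possibly one line of site guidance. The worsening clause will raise reported AE rates slightly. The SAP introduction says the plan is finalized before database lock, so the changes can be made at that point. If sites already open new records at worsening, the SAP 4.2.1 text only documents what is done.
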